4. DMC

2.

There were no DMC reviews planned for the OLP.

5. Patient Disposition

Patient disposition information will only include subjects who participated the OLP.

6. **OLP Baseline**

Baseline for efficacy analyses:

Core baseline: The last assessment prior to/on first dose date in Core Period.

The full set of the efficacy endpoints will be derived based on Core baseline.

Baseline for safety analyses:

The adverse events (AEs) will be summarized per Section 8.

For non-AE safety endpoints, definition of Baseline will not change (SAP v2.0 Section 5.1)

7. Efficacy Analyses

The efficacy measurements will be summarized by parent study treatment group at each OLP visit in the OLP ITT population. Non-responder imputation (NRI) will be used as the primary method for addressing missing binary outcomes. No treatment failure rule will be applied in the OLP, as per its defined in Section 6.19 (SAP v2.0).

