- e. Patients who continue past Week 8 in the OLP will have the Additional OLP Visit assessments performed at 12-week intervals throughout the OLP. The OLP will continue for up to 6 years, or until marketing approval of RPC1063 for UC in the country of the clinical site (estimated to be in 2019), or the completed transition of patients to Study RPC01-3102, or until the Sponsor discontinues the development program.
- f. For females of childbearing potential only, serum beta human chorionic gonadotropin (hCG) at screening is required and a urine beta hCG is required at each visit. Between scheduled visits, monthly urine pregnancy tests should be performed by the patient. If a urine pregnancy test is positive, the Investigator will instruct the patient to suspend further RPC1063 dosing, if applicable, and schedule a follow-up appointment as soon as possible. A serum pregnancy test will be performed for confirmation, including after the 90-day Safety Follow-up Visit, if needed.
- g. Includes weight. The complete physical examination will include a full examination of the skin for lesions as well as a check for visual symptoms (i.e., blurred vision or decreased visual acuity).
- h. An interim physical examination will be conducted at Visit 5OLP and 30-day Safety Follow-up Visit. The interim PE will include areas with previously noted abnormalities and/or that are associated with any new complaints from the patient. The interim PE will also include a check for visual symptoms (i.e., blurred vision or decreased visual acuity).
- i. DLCO, if applicable, will be done at End of Open-Label/ET.
- j. The PK blood sample on Week 8 should be trough level, taken just prior to dose administration. The blood sample on End of Open-label Visit/ET should be taken 2-6 hours after dosing. The actual time of investigational drug administration for all visits with PK evaluation will be recorded on the dosing log. The blood sample at the 30-day and 90-day Safety Follow-up Visits can be collected at any point during the visit. An additional PK sample will be obtained for patients with any AE resulting in unblinding, discontinuation, or SAE.
- k. For patients who continue past Week 8 in the OLP, an endoscopy will be performed at Week 56OLP and a full Mayo score will be calculated at that time.
- l. At End of Open-Label or ET Visit sigmoidoscopy should be performed either on day of visit or no more than 7 days prior to the visit date.

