8. DEVIATIONS FROM PROTOCOL

The analyses of the following endpoints specified in the protocol are not performed due to collected samples have not been analyzed at the time of database lock.

- Proportion of patients with histologic Remission at Week 8 for exploratory objectives and exploratory efficacy endpoints.
- Plasma protein biomarkers (cytokines, chemokines, other inflammatory proteins) as PD endpoint.

STATISTICAL ANALYSIS PLAN - OPEN LABEL PERIOD ADDENDUM

Title: A Phase 2, multi-center, randomized, double-blind, placebo-

controlled parallel-group study to evaluate the clinical efficacy and

safety of induction therapy with RPC1063 in patients with

moderately to severely active ulcerative colitis

Protocol: RPC01-202

Sponsor: Celgene International II Sàrl (see appended signature page)

[name] [name]

[contact]

Date: October 15, 2019

Status: Addendum to Version 2.0

CONFIDENTIAL

This document is a confidential communication of Receptos. Acceptance of this document constitutes agreement by the recipient that no unpublished information contained herein shall be published or disclosed without prior written approval, except that this document may be disclosed to the appropriate Institutional Review Board(s)/Independent Ethics

Committee(s) under the condition that they keep it confidential.

TABLE OF CONTENTS

SIGNA	ATURES	2
TABLE	E OF CONTENTS	3
LIST O	OF ABBREVIATIONS	4
1.	Introduction	5
2.	Study Design	5
3.	Analysis Cohorts	5
4.	DMC	5
5.	Patient Disposition	5
6.	OLP Baseline	5
7.	Efficacy Analyses	6
7.1.	Endpoints	6
7.2.	Mayo Score at the End of OLP	6
7.3.	Visit Windows	7
8.	Safety Analyses	8
9.	Guideline on Missing Date Imputation	8

LIST OF ABBREVIATIONS

AE adverse event DEF definition

DMC data monitoring committee

IP Induction Period ITT intent-to-treat

[figure not shown]
MP Maintenance Period

NRI Non-responder imputation
OLP Open-Label Treatment Period

SAE serious adverse event SAP statistical analysis plan

UC ulcerative colitis

1. Introduction

Study Design

3. Analysis Cohorts

- Intent-to-Treat (ITT) Analysis Cohorts will be labeled by randomized treatment in the parent study for all subjects who received at least one dose of RPC1063 1mg in OLP.
- Safety Analysis Cohorts will be labeled by actually received treatment in the parent study for all subjects who received east one dose of RPC1063 1mg in OLP.

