7.1. Endpoints

Complete Mayo score: The Full Mayo score in SAP v2.0.

The 9-point Mayo score: The sum of the Rectal Bleeding subscore, Stool Frequency subscore, and the Endoscopy subscore. The 9-point Mayo score has a range of 0-9 points.

OLP Efficacy Endpoints

Clinical Remission

- Four-component Mayo clinical remission: Complete Mayo score of <=2 points with no individual subscore of >1 point
- Three-component Mayo clinical remission: Rectal bleeding subscore=0 and stool frequency subscore <=1 (and a decrease of >=1 point from the baseline stool frequency subscore), and endoscopy subscore <=1

Clinical Response

- Four-component Mayo clinical response: Reduction from baseline in complete Mayo score of >=3 points and reduction from baseline in complete Mayo score of >=30%, and (reduction in rectal bleeding subscore of >=1 point or a rectal bleeding subscore of <=1 point)
- Three-component Mayo clinical response: Reduction from baseline in the 9-point Mayo score of >=2 points and Reduction from baseline in the 9-point Mayo score >=35%, and (reduction from baseline in the rectal bleeding subscore of >=1 point or a rectal bleeding subscore of <=1 point).

Mucosal Healing

- Mucosal Healing is defined as an Endoscopic subscore of ≤ 1 point
- Mucosal healing (alternative definition): Endoscopy subscore of <=1 point and a Geboes index score <2.0

Histological remission

• Histological remission is defined as Geboes index score < 2.0.

Analysis visit windows defined in Section 7.3 will be applied on all efficacy analyses.

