7.2. Mayo Score at the End of OLP

The analyses will be carried out when all patients have completed (or would have been eligible to complete) the OLP of the study. The mayo score will be summarized using descriptive statistics.

The proportion of patients in clinical remission, clinical response, and with mucosal healing will be descriptively summarized at each visit window defined in Section 7.3 in the OLP ITT population.

The proportion of patients in partial Mayo clinical remission and in partial Mayo clinical response will be descriptively summarized for each OLP visit in the OLP ITT population.

The proportion of patients in clinical remission (for all bullet definitions listed in Section 7.1), in clinical response (for all bullet definitions listed in Section 7.1), and with mucosal healing will also be descriptively summarized as described above in the same subgroups as the Core period in the OLP ITT population.

- Prior anti-TNFα use (yes vs. no)
- Age (\leq median vs. \geq median)
- Sex (Female vs. Male)
- Disease localization (Left side vs. Extensive)
- Baseline disease activity (Mayo score using the central endoscopy read $\leq 8 \text{ vs.} > 8$)

The proportion of patients in clinical remission (for all definitions), in clinical response (for all definitions), and with mucosal healing will be descriptively summarized as described above in the OLP ITT population using:

- Observed cases
- NRI

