7.3. Visit Windows

Post-OLP-Baseline visits (scheduled or unscheduled) during OLP will be mapped to an analysis visit based on the windowing algorithm below. If a visit cannot be mapped to any analysis visit, then the analysis visit will be set to missing and the data of interest will be excluded from summaries. If multiple visits containing the same data of interest can be mapped to the same analysis visit, the visit closest to the target day will be used in the analysis. In the event that two or more visits are equidistant to the target day, the later visit will be used in the analysis. If the two visits are on the same day, then the visit with the worst result will be used in the analysis.

Visit	Target Day	Analysis Visit Window for partial Mayo score	Analysis Visit Window for Complete Mayo Score, 9-point Mayo Score and Geboes Index
		(+/- 6 weeks)	(+/- 24 weeks)
Day 1OLP	1	N/A	N/A
Week 4OLP	36	(19-50)	N/A
Week 8OLP	64	(51 - 106)	N/A
Week 20OLP	148	(107 - 190)	N/A
Week 32OLP	232	(191 - 274)	N/A
Week 44OLP	316	(275 - 358)	N/A
Week 56OLP	400	(359 - 442)	(232 - 568)
Week 68OLP	484	(443 - 526)	N/A
Week 80OLP	568	(527 - 610)	N/A
Week 92OLP	652	(611 - 694)	N/A

Week 104OLP	736	(695 - 778)	(569 - 904)
Week 116OLP	820	(779 - 862)	N/A
Week 128OLP	904	(863 - 946)	N/A
Week 140OLP	988	(947 - 1030)	N/A
Week 152OLP	1072	(1031 - 1114)	(905 - 1240)
Week 164OLP	1156	(1115 - 1198)	N/A
Week 176OLP	1240	(1199 - 1282)	N/A
Week 188OLP	1324	(1283 - 1366)	N/A
Week 200OLP	1408	(1367 - 1450)	(1241 - 1576)
Week 212OLP	1492	(1451 - 1534)	N/A
Week 224OLP	1576	(1535 - 1618)	N/A
Week 236OLP	1660	(1619 - 1702)	N/A
Week 248OLP	1744	(1703 - 1786)	(1577 - 1912)
Week 260OLP	1828	(1787 - 1870)	N/A
Week 272OLP	1912	(1871 - 1954)	N/A
Week 284OLP	1996	(1955 - 2038)	N/A
Week 296OLP	2080	(2039 - 2122)	(1913 - 2248)
Week 308OLP	2164	(2123 - 2206)	N/A
Week 320OLP	2248	(2207 - 2290)	N/A

8. Safety Analyses

AEs will be recorded from the time written informed consent is signed through the 90-day safety Follow-up visit to ensure adequate collection of adverse events that could be associated with investigational drug.

Treatment-emergent adverse events include adverse events that started between the date of first dose of OLP and 90-day safety Follow-up visit after the date of last dose.

9. Guideline on Missing Date Imputation

The following missing data imputation rules will be applied to the OLP analyses.

Medication Dates:

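### The OLP addendum applies non-responder imputation to endoscopy- and biopsy-based endpoints at Weeks 104 to 248OLP, where the protocol schedules no endoscopy or biopsy for patients who continue

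*SAP*

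**What the plan says.** **Schedule (Protocol Table 2).** Endoscopy, full Mayo score and colonic biopsy are marked in the additional OLP visits column with footnote k only. For patients who go on past OLP Week 8, that footnote says "an endoscopy will be performed at Week 56OLP and a full Mayo score will be calculated at that time". The one other scheduled occasion is the exit visit, where footnote l reads: "At End of Open-Label or ET Visit sigmoidoscopy should be performed either on day of visit" (or within the week before). Biopsy is marked at that visit too. The partial Mayo score is collected at the 12-weekly visits.

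**Analysis (SAP OLP addendum).**
- Section 3 defines the OLP ITT cohorts "for all subjects who received at least one dose of RPC1063 1mg in OLP".
- Section 7 sets the missing-data rule: "Non-responder imputation (NRI) will be used as the primary method for addressing missing binary outcomes".
- Section 7.1 adds: "Analysis visit windows defined in Section 7.3 will be applied on all efficacy analyses". It defines the three-component (9-point) endpoints, two versions of mucosal healing and Geboes histological remission. For the four-component score it says only "Complete Mayo score: The Full Mayo score in SAP v2.0".
- Section 7.2 says that the proportions in remission, in response and with mucosal healing "will be descriptively summarized at each visit window defined in Section 7.3 in the OLP ITT population". It also plans observed-case versions, and partial Mayo remission and response at each OLP visit.
- Section 7.3 gives windows for complete Mayo, 9-point Mayo and Geboes at Weeks 56, 104, 152, 200, 248 and 296OLP. On which visits count, it says: "scheduled or unscheduled) during OLP will be mapped to an analysis visit".

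No visible text exempts an assessment that was never scheduled from the imputation.

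**The concern.** Non-responder imputation is defensible when a patient has dropped out or missed an assessment that was due. Here it also reaches patients who are still on treatment and have followed the schedule exactly. In a late window such a patient has no endoscopy because the protocol did not ask for one, and the missing value is turned into a failure.

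The late-window rates would then largely reflect when patients leave the OLP, since leaving is what triggers an endoscopy. A drop after Week 56OLP could be read as loss of long-term effect. The same distortion would pass into the displays by parent-study treatment group and by subgroup.

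**Working it through.** **Inputs.** Target days and windows: addendum 7.3. Visit tolerance of 14 days either way for the 12-weekly OLP visits, and footnotes e, k and l: Protocol Table 2. Six-year limit on the OLP: Protocol 9.1 and Table 2 footnote e. Mayo scoring rules: SAP 5.2.2 and 6.4.

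**1. Reproduce the windows.** Target day = 7 × week + 8; half-width = 24 × 7 = 168 days. From the second window on, the lower limit is moved up one day to avoid overlap. All six rows agree with the addendum.

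| OLP week | Target day | Stated window (days) | Scheduled endoscopy or biopsy for a patient who continues through the window |
|---|---|---|---|
| 56 | 400 | 232–568 | Yes (footnote k) |
| 104 | 736 | 569–904 | None |
| 152 | 1072 | 905–1240 | None |
| 200 | 1408 | 1241–1576 | None |
| 248 | 1744 | 1577–1912 | None |
| 296 | 2080 | 1913–2248 | See step 3 |

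**2. Place the Week 56OLP endoscopy.** Day 400 ± 14 gives Days 386–414. This lies wholly inside 232–568, so it cannot supply any later window.

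**3. Week 296OLP.** Six years is 6 × 365.25 = 2191.5 days, inside 1913–2248. If the cap is kept, anyone still on treatment has an End of OLP visit, with endoscopy and biopsy, within that window. The addendum table nevertheless runs on to Week 320OLP (target day 7 × 320 + 8 = 2248; partial Mayo window to Day 2290), so it leaves open that patients stay longer.

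**4. Upper bound from scheduled data.** Let x be the share of the OLP ITT population with a scheduled endoscopy in a given late window.
- The NRI rate in that window cannot exceed x.
- The only scheduled endoscopy after Week 56OLP is at End of OLP/ET, so each patient contributes to at most one window, and the x values sum to at most 1.
- Weeks 104 to 248 (four windows): average NRI rate ≤ 1/4 = 25%.
- With Week 296 included (five windows): average ≤ 1/5 = 20%.

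This holds even if every patient is a success. It limits the average only; a single window can be higher if exits cluster there. Unscheduled endoscopies could add to it.

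**5. One patient.** Take a patient healed at Week 56OLP who stays on treatment and is healed at an exit endoscopy on Day 1744. Mucosal healing, read literally, is: Week 56 yes; Weeks 104, 152 and 200 no; Week 248 yes. The changes come from the schedule alone.

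**6. Which endpoints are reached.**
- *Three-component Mayo.* It needs the endoscopy subscore. The addendum gives no missing-subscore rule for it, and SAP 6.4 names only the total and partial Mayo scores. Read literally, NRI applies.
- *Mucosal healing, both definitions, and Geboes remission.* These need endoscopy, biopsy or both. Read literally, NRI applies. Section 7.2 does not name histological remission, which is reached only through the general sentences in Sections 7 and 7.1.
- *Four-component Mayo.* SAP 6.4 needs two of the four subscores and fills a missing one from the latest earlier visit that has it. SAP 5.2.2 derives the score at visits with an endoscopy. If 5.2.2 governs, NRI applies. If 6.4 governs, the Week 56OLP endoscopy subscore is reused.
- SAP 5.2.2 lists mucosal healing under the full Mayo score, so the same question arguably extends to it.

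**7. Age of a reused Week 56OLP subscore at the target days.** Week 104: (736 − 400)/7 = 48 weeks. Week 248: (1744 − 400)/7 = 192 weeks.

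**The case against.** **Hidden text.** Addendum Sections 1 and 2 show headings but no text. A study-design section is a natural place for an assessment schedule or an evaluability rule, and the 48-week window spacing would fit periodic endoscopy. This stands as a limit on certainty. It does not remove the conflict with Protocol Table 2 as it reads.

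**Mitigation already planned.** Observed cases and partial Mayo summaries are in the plan, and SAP 6.1 uses non-missing denominators, so the number examined should be visible. That is fair, and it softens the effect. But NRI is named as primary, and late-window observed data come mainly from patients who are leaving or having an unscheduled assessment, for example for suspected relapse (Protocol 10.6).

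**Carry-forward.** If SAP 6.4 extends to these endpoints, the continuing patient is not imputed as a nonresponder. This stands for four-component Mayo and arguably for mucosal healing. The difficulty then becomes an endoscopy subscore 48 weeks old or more.

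**Low rates are partly legitimate.** Earlier discontinuations are properly nonresponders under NRI, so the gap between 25% and 100% is not all distortion. This also stands.

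**Stronger readings to resist.** A reader might put a figure on the Week 104OLP deficit. That needs exit rates, and the documents give none; they also plan transfers to Study RPC01-3102 without giving a date, and these would bring exit endoscopies into the windows. A reader might also place Week 296OLP on the same footing as the earlier windows, or suppose that all late rates must be near zero. The six-year cap and the exit endoscopies rule out both.

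**Conclusion.** The conflict holds as the visible text stands. For a patient who continues through the windows at Weeks 104, 152, 200 and 248OLP, the primary method scores a failure where the protocol scheduled no assessment. This is firmest for the three-component Mayo endpoints. It holds on a literal reading for both mucosal-healing definitions and, where reported, for Geboes remission. It is conditional for four-component Mayo, and for Week 296OLP.

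The only size the documents support is the 25% ceiling on the average late-window NRI rate (20% over five windows). That ceiling rests on the Table 2 schedule and on scheduled data alone. The size of the distortion in any one window cannot be derived.

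The consequence is confined to descriptive, uncontrolled OLP summaries. A reader might infer that the trial's efficacy conclusions are in doubt; the Week 8 and Week 32 analyses use their own scheduled endoscopies and are untouched. Confidence is medium, because of the blank addendum sections and the unsettled subscore rule.

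**What to change.** In addendum Sections 7, 7.2 and 7.3:

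1. Apply NRI to endoscopy- and biopsy-based endpoints only at Week 56OLP and at a separate End of OLP/ET time point.
2. For later windows, drop the NRI summaries of these endpoints. Show observed data only, with the number examined and the number still in the OLP, labelled as mainly exit or unscheduled endoscopies.
3. Rely on the partial Mayo summaries already planned for later time points.
4. State whether SAP 6.4 or SAP 5.2.2 governs the endoscopy subscore in the OLP, and do not carry the Week 56OLP endoscopy into later windows.

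If the text of Sections 1 or 2 already holds a schedule or evaluability rule, a cross-reference to it and reconciliation with Protocol Table 2 are needed instead.

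The cost is wording and fewer tables, with no new data collection. The downside is that no NRI-based endoscopic estimate remains after Week 56OLP other than at exit, which is all the schedule supports.

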All patients who complete the IP and are responders (see [Section 13.8](#)) at Week 8 of the IP will enter the 24-week MP. Patients will continue to receive the same investigational drug in the MP as received during the IP, and individual patient treatment will remain blinded until all patients have reached Week 32. The last visit in the MP will occur at Week 32. Patients

who complete the MP will be given the option to participate in the OLP. Patients that enter the MP and experience disease relapse will have the option to enter the OLP.

Optional Open-Label Treatment Period (OLP)

Patients who complete the IP and are non-responders at Week 8 and those that complete the MP or experience disease relapse during the MP will have the option to enter the OLP. All patients in the OLP will receive daily study treatment with RPC1063 1 mg. There will be an 8-day dose escalation regimen consisting of 4 days of treatment with RPC1063 0.25 mg, followed by 3 days of treatment with RPC1063 0.5 mg, followed by RPC1063 1 mg.

Patients who have not shown clinical improvement 8 weeks after initiation of the OLP should discontinue from the study. Eligible patients will be transitioned into the Phase 3 open-label extension UC Study RPC01-3102 and will be able to immediately enter the study (without completing the 30-day or 90-day Safety Follow-up Visits). The OLP will continue for up to 6 years, or until marketing approval of RPC1063 for UC in the country of the clinical site (estimated to be in 2019), or completed transition of patients to Study RPC01-3102, or until the Sponsor discontinues the development program.

Safety Monitoring/Follow-up

Potential AEs of interest that may be a consequence of S1P₁ modulation will be closely monitored during the study. These AEs include bradycardia, heart conduction abnormalities, pulmonary toxicity, macular edema, cutaneous malignancy, serious or opportunistic infection, and hepatotoxicity. A DMC for the study will perform safety reviews periodically, approximately 4 times a year until the end of the Maintenance Period.

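### Nonresponder imputation in the open-label period has no visible exception for visits that could not take place because the period had closed or the patient had moved to RPC01-3102, so late-visit rates fall for administrative reasons

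*SAP*

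**What the plan says.** **Missing-data rule.** Section 7 (Efficacy Analyses) of the OLP addendum says: "Non-responder imputation (NRI) will be used as the primary method for addressing missing binary outcomes". The same paragraph sets the scope: "The efficacy measurements will be summarized by parent study treatment group at each OLP visit in the OLP ITT population".

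**Denominator.** Section 3 of the addendum defines the OLP ITT cohorts "for all subjects who received at least one dose of RPC1063 1mg in OLP". That set does not change from visit to visit.

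**Endpoints and visits.** Section 7.2 adds: "The proportion of patients in partial Mayo clinical remission and in partial Mayo clinical response will be descriptively summarized for each OLP visit". No separate missing-data rule is given for these partial Mayo endpoints. Section 7.3 lists visits out to Week 320OLP, target Day 2248, with a partial Mayo window of Days 2207 to 2290. Protocol Table 2, footnote e, has the "Additional OLP Visit assessments performed at 12-week intervals throughout the OLP", so a partial Mayo score is scheduled at each of these visits.

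**Planned exits.** Protocol Section 9.1 says: "The OLP will continue for up to 6 years, or until marketing approval of RPC1063 for UC in the country of the clinical site". It also names completed transition to RPC01-3102 and the sponsor stopping development as end points. On rollover it says: "Eligible patients will be transitioned into the Phase 3 open-label extension UC Study RPC01-3102".

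**Other displays.** Section 7.2 also plans observed-case summaries for clinical remission, clinical response and mucosal healing.

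**The concern.** Nonresponder imputation is a sensible conservative rule when a patient stops because the drug does not work or is not tolerated. It is not sensible for a visit that could never be held. A patient in remission who moves to RPC01-3102 at Week 104OLP has no Week 116OLP assessment in this study. Under the rule as written that patient is a nonresponder at Week 116OLP and at every later visit.

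The protocol asks patients without clinical improvement 8 weeks into the OLP to discontinue. Those who leave later for administrative reasons may therefore include many who are doing well. Readers will look to the primary OLP display for evidence that benefit lasts. At late visits that display would mix loss of response with closure of the study, and nothing in it would tell the two apart.

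**Working it through.** **1. The visit table.** Target day = 7 × (week + 1) + 1. Week 56OLP: 7 × 57 + 1 = 400. Week 320OLP: 7 × 321 + 1 = 2248. The formula reproduces all 28 post-baseline target days in addendum Section 7.3. For the 12-weekly visits from Week 20OLP the partial Mayo window opens 41 days before target: 2248 − 41 = 2207, as printed.

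**2. The 6-year limit.** 6 × 365.25 = 2191.5 days. The Week 320OLP window opens 2207 − 2191.5 = 15.5 days later. If the limit is kept, nobody can be assessed in that window, and imputation returns 0% whatever the true response. The Week 308OLP window (Days 2123 to 2206) can still be reached.

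**3. Size of the dilution.** Let r be the true rate and f the share of the OLP ITT that has left administratively before the window. If exit is unrelated to response and nothing else is missing, the reported rate is (1 − f) × r. The documents give neither r nor f, so both are assumptions:

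| True rate | f = 10% | 25% | 50% | 75% | 90% |
|---|---|---|---|---|---|
| 40% | 36% | 30% | 20% | 10% | 4% |
| 60% | 54% | 45% | 30% | 15% | 6% |
| 80% | 72% | 60% | 40% | 20% | 8% |

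**4. When it starts.** From the protocol: study dates October 2012 to December 2019 (Synopsis), about 18 months of enrolment (Section 9.4), and Week 8 and Week 32 visits at Days 64 and 232 (Table 1). Assumed: randomisation uniform over 18 months from early November 2012, OLP entry at Day 64 or Day 232, no other dropout, and one common closure or rollover date. The table gives the share still able to reach the partial Mayo window, Day 64 entrants / Day 232 entrants:

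| Closure or rollover | Week 152 | Week 200 | Week 248 | Week 272 | Week 296 | Week 308 | Week 320 |
|---|---|---|---|---|---|---|---|
| End 2019 | 100/100% | 100/100% | 100/100% | 100/93% | 93/63% | 78/47% | 0/0% |
| End 2018 | 100/100% | 100/100% | 88/57% | 57/27% | 27/0% | 11/0% | 0/0% |
| End 2017 | 100/100% | 83/52% | 21/0% | 0/0% | 0/0% | 0/0% | 0/0% |
| End 2016 | 77/47% | 16/0% | 0/0% | 0/0% | 0/0% | 0/0% | 0/0% |

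The reported rate is cut by the same factor.

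**5. Comparing denominators.** Take 100 OLP patients (assumed): 60 in stable remission and 40 who stopped early for lack of effect. Half the sites then transition, taking 30 of the 60 remitters. Those sites also held 20 of the 40 early dropouts.

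- All-patient nonresponder imputation: 30/100 = 30%.
- Observed cases: 30/30 = 100%.
- Removing only the rollovers: 30/(100 − 30) = 30/70 = 43%.
- Removing everyone at transitioned sites, dropouts included: 30/(30 + 20) = 60%, the true rate.

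**The case against.** **The rule may not be meant this way.** The addendum does not say whether a visit that was never due counts as missing. The text of its Sections 1 and 2 is not available here, so an exception there cannot be excluded. This stands as a limit on the point. But Section 7 carries the operative rule, and it has no exception. Section 7.2's phrase about patients who would have been eligible to complete the OLP governs when the analysis is run, not who is in the denominator.

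**Other displays help.** Observed cases are planned beside nonresponder imputation, and SAP Section 6.11 tabulates withdrawal reasons by period. Both are useful. Observed cases, however, drop patients who left for lack of effect or adverse events, so they err in the other direction. Section 7.2's list might be read to include partial Mayo, since it refers to all definitions, but it does not name it.

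**Removing rollovers alone is biased.** This is right, as step 5 shows (43% against a true 60%). A sound fix must apply the same cut-off to earlier dropouts.

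**Stronger readings that the documents do not support.**

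- A reader might infer that leavers are classed as treatment failures. They are not: Section 7 switches the treatment failure rule off in the OLP. They are nonresponders by imputation.
- A reader might infer that all visits from about Week 272OLP are automatic nonresponse. Under closure at end-2019 that is true only of the latest entrants; 93% and 63% of the two entry groups can still reach Week 296OLP.
- A reader might infer a known bias between parent-study arms. Entry times differ by 232 − 64 = 168 days, two 12-weekly visits, but the documents give no OLP entry numbers by arm and the addendum describes no between-arm test. No claim is made about its size.

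**Conclusion.** The concern holds. A fixed OLP ITT denominator, primary nonresponder imputation at every visit and planned administrative exits together push late-visit rates down for reasons unrelated to the drug, partial Mayo endpoints included. At Week 320OLP the rate is forced to 0% if the 6-year limit is kept, and this needs no assumption about response or rollover.

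Elsewhere the direction follows from the rule, but the size and onset cannot be computed from the documents because rollover timing and numbers are not given. Under the stated entry assumptions, closure at end-2019 confines the effect to Week 272OLP onward; earlier rollover brings it forward.

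The OLP analyses are open-label and descriptive. No hypothesis test, alpha or core-study endpoint is affected. What suffers is the interpretation of long-term response.

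**What to change.** In addendum Section 7, define the primary denominator for nonresponder imputation at each visit as OLP ITT patients whose potential follow-up reaches that visit's window. Potential follow-up runs from the patient's OLP start date to the earliest administrative end date that applies: OLP closure, local approval, transition to RPC01-3102 at the site or in the country, or the 6-year limit.

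- Apply the cut-off identically to patients who stayed, rolled over or dropped out earlier. Inside it, keep nonresponder imputation for all non-administrative missing data.
- Where rollover dates vary within a site, use one common site date, the first rollover there, so that rollovers are not removed selectively.
- Show the number eligible and the number observed at each visit, and drop the Week 320OLP row.
- Keep all-patient nonresponder imputation and observed cases as sensitivity displays, and extend observed cases explicitly to partial Mayo.

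**Cost.** This needs revised wording and one derived eligibility flag per patient and visit. The flag uses OLP start dates and closure or transition dates, so it does not depend on an exit-reason category; protocol Section 9.7.1 lists none for rollover. Late-visit denominators become smaller and less precise, and data after a site's cut-off move to the sensitivity displays. The approach assumes that a site's transition date is unrelated to how its patients were responding.
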